## 5.2 Analysis Populations

The analysis populations for cardiodynamic ECG assessment are defined as follows (Table 1).

**Table 1 Analysis populations for cardiodynamic ECG assessment**

Population	Subjects
Safety population	All subjects enrolled in the study who receive at least 1 dose of study drug (LOXO-292, moxifloxacin, or placebo).
PK population	All subjects who receive a dose of LOXO-292 or moxifloxacin and have at least 1 evaluable PK plasma concentration of LOXO-292 or moxifloxacin.
Cardiodynamic population	All subjects in the Safety population with measurements at baseline as well as on-treatment with at least 1 post-dose time point with a valid $\Delta QTcF$ value. The Cardiodynamic population will be used for the by-time point and categorical analyses of the cardiodynamic ECG parameters.
C-QT population	All subjects who are in both the PK and Cardiodynamic populations with at least 1 pair of post-dose PK and QTcF data from the same time point as well as subjects in the Cardiodynamic population who received placebo. The C-QT population will be used for the concentration-QTc analysis. This population will be defined separately for LOXO-292 and for moxifloxacin.

## 5.3 Baseline

For all continuous ECG parameters from each period, baseline is defined as the average of the measured ECG intervals from the 3 pre-dose time points (0.75, 0.5, and 0.25 hours before dosing) on Day 1 for the respective period.

## 5.4 QT Correction Methods

The QT and RR value for each beat will be used for HR correction. Replicate ECGs will be extracted in up to 10 replicates from each nominal time point prespecified in the protocol. The median value from each extracted replicate from evaluable beats will be calculated, and then the average of all available medians (minimum 3 medians) from a nominal time point will be used as the subject's reportable value at that time point.

The Fridericia's correction QTcF is defined as  $QTcF = QT/RR^{1/3}$ .

In case a substantial heart rate effect (i.e., largest mean  $\Delta\Delta HR > 10$  bpm) is observed, additional QT correction methods, including the population heart rate-corrected QT interval (QTcP as described by Tornoe et al), will be considered.

## 6 Analyses

### 6.1 Carryover Effect Test

Before the concentration-QTc analysis in Section 6.2 is performed, it is necessary to test the carryover effect, even the possibility that some subjects receiving placebo may have small residual exposures to LOXO-292 present. A mixed-effect repeated measures model will be considered with  $\Delta QTcF$  as the dependent variable; period, time (i.e., post-dose time points), treatment (therapeutic dose of LOXO-292, supratherapeutic dose of LOXO-292, and placebo), time-by-treatment interaction, period-by-treatment interaction, period-by-time interaction, and period-by-treatment-by-time as fixed effects, and baseline QTcF as a covariate. An unstructured covariance matrix will be specified for the repeated measures at post-dose time points for subject within treatment period. If the model with an unstructured covariance matrix fails to converge, other covariance matrices such as compound symmetry and autoregressive will be considered. The model will also include a subject-specific random effect. If the period-by-treatment interaction (and period-by-treatment-by-time interaction if necessary) is not statistically significant at the significance level 5%, this indicates that there is no carryover effect. Then the proposed concentration-QTc analysis (as well as by-time point analysis and categorical analysis) will be performed, and zero will be substituted for concentrations below the quantification limit of the assay and for concentrations from subjects who received placebo. Otherwise, a sensitivity analysis(es) of concentration-QTc, by-time point, and categorical analyses will be performed by excluding period(s) with observed non-zero concentrations at baseline for subjects receiving placebo. Additional sensitivity analyses may exclude subjects with more than extremely low LOXO-292 concentrations.

### 6.2 Concentration-QTc Analysis (Analysis of Primary Endpoint)

The concentration-QTc analysis will be based on the C-QT population. The relationship between LOXO-292 plasma concentration and change-from-baseline QTcF ( $\Delta QTcF$ ) will be quantified using a linear mixed-effects model with  $\Delta QTcF$  as the dependent variable, LOXO-292 plasma concentration as the explanatory variate (0 for placebo), centered baseline QTcF (i.e., baseline QTcF for individual subject subtracting the population mean baseline QTcF for all subjects in the same period) as an additional covariate, study treatment (active = 1 or placebo = 0), and time (i.e., post-dose time point) as categorical factors, and a random intercept and slope per subject (Garnett et al). The degrees of freedom for the model estimates will be determined by the Kenward-Roger method. From the model, the slope (i.e., the regression parameter for the concentration) and the treatment effect-specific intercept (defined as the difference between active and placebo) will be estimated together with the 2-sided 90% CI. The estimates for the time effect will be reported with degrees of freedom and SE.

The geometric mean of the individual  $C_{max}$  values for LOXO-292 plasma concentrations for subjects in each of the LOXO-292 dose groups will be determined, respectively. The predicted effect and its 2-sided 90% CI for  $\Delta\Delta QTcF$  (i.e., slope estimate  $\times$  concentration + treatment effect-specific intercept) at this geometric mean  $C_{max}$  will be obtained. If the upper bound of the 2-sided 90% CI of the model-predicted QTc effect is below 20 ms at clinically relevant plasma levels of LOXO-292, it will be concluded that LOXO-292 does not cause clinically concerning QTc prolongation within the observed plasma concentration ranges.

The plot of the observed median-quantile LOXO-292 concentrations and associated mean placebo-adjusted  $\Delta QTcF$  (i.e.,  $\Delta\Delta QTcF$ ) with 90% CI adjusted for diurnal effects, together with the regression line presenting the predicted  $\Delta\Delta QTcF$  (90% CI) (as described by Tornoe et al) will be used to evaluate the adequacy of the model fit to the assumption of linearity and the impact on quantifying the concentration-QTc relationship. The observed  $\Delta QTcF$  values from the active groups will be adjusted by the estimated time effect from the concentration-QTc model (i.e. the estimated diurnal effect under the placebo treatment). The individually estimated placebo-adjusted  $\Delta QTcF_{i,j}$  equals the individual  $\Delta QTcF_{i,j}$  for subject  $i$  administered with LOXO-292 at time point  $j$  minus the estimation of time at time point  $j$  (i.e., time effect). Additional plots will be used to validate the model assumptions. For evaluation of the heart rate-corrected QT interval, a scatter plot and quantile plot of QTcF and RR intervals by treatment with a regression line and a linear mixed-effects line (90% CI), respectively, will also be given. Exploratory analyses (via graphical displays and/or model fitting) will also include accounting for a delayed effect (hysteresis) and the justification for the choice of pharmacodynamics model (linear versus nonlinear).

The SAS code for the concentration-QTc analysis is as follows:

```
PROC MIXED DATA=PKPD method=reml;
CLASS SUBJID TIME;
MODEL DQTC=TRT CONC TIME CBASE/ solution cl noint alpha=0.1 alphap=0.1 COVB DDFM=KR;
RANDOM INT CONC /type=UN SUBJECT=SUBJID s;
ESTIMATE 'Pred Mean Diff for T1' TRT 1 CONC &GeoMeanCmax_1 / CL ALPHA=0.1;
ESTIMATE 'Pred Mean Diff for T2' TRT 1 CONC &GeoMeanCmax_2 / CL ALPHA=0.1;
RUN;
```

Where PKPD=C-QT population, SUBJID=subject number, TRT=treatment (active=1 or placebo=0), TIME=nominal time point, CONC=plasma concentration of LOXO-292, CBASE=centered baseline QTcF, T1= therapeutic dose of LOXO-292, T2 = supratherapeutic dose of LOXO-292, GeoMeanCmax\_1=geometric mean  $C_{max}$  for therapeutic dose of LOXO-292, GeoMeanCmax\_2=geometric mean  $C_{max}$  for supratherapeutic dose of LOXO-292, and DQTC= $\Delta QTcF$ .

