### 6.2.2 Appropriateness of a Linear Model

To assess the appropriateness of a linear model, normal Q-Q plots for the standardized residuals and the random effects, and plots of standardized residuals versus concentration, fitted values, centered baseline QTcF, nominal time, and active treatment will be produced. Scatter plots for standard residuals versus continuous covariates and box plots for standard residuals versus discrete covariates will be provided. The scatter plots of standardized residuals versus concentration, and centered baseline QTcF by LOESS fitting (i.e., locally weighted scatter plot smoothing (as described by Cleveland) will also be produced with optimal smoothing parameters selected by the Akaike information criterion with a correction. A scatter plot of observed concentration and  $\Delta$ QTcF with a LOESS smooth line with 90% CI and a linear regression line will also be provided to check the assumption of a linear concentration-QTc relationship. If there is an indication that a linear model is inappropriate, additional models will be fitted, in particular an  $E_{max}$  model. The concentration-QTc analysis will then be repeated for the model found to best accommodate the nonlinearity detected.

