14.2.3.1.9.2	Assay sensitivity analysis of moxifloxacin and associated $\Delta\text{QTcF}$ prolongation	Fixed-effect estimations and corresponding $P$ values will be given (Section 6.3).
14.2.3.1.10.1	Predicted $\Delta\Delta\text{QTcF}$ interval at geometric mean peak LOXO-292 concentration	Section 6.2.
14.2.3.1.10.2	Predicted $\Delta\Delta\text{QTcF}$ interval at geometric mean peak moxifloxacin concentration	Section 6.3.

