## 8.2 Figures

Number	Title	Comments
14.2.3.2.1	Absolute QTcF across time points	Mean and 90% CI from descriptive analysis will be given by treatment.
14.2.3.2.2.1- 14.2.3.2.2.4	Change-from-baseline QTcF, HR, PR, and QRS ( $\Delta\text{QTcF}$ , $\Delta\text{HR}$ , $\Delta\text{PR}$ , and $\Delta\text{QRS}$ ) across time points	LS mean and 90% CI from the statistical modeling will be shown by treatment for each parameter (Section 6.5).
14.2.3.2.3.1- 14.2.3.2.3.4	Placebo-corrected change-from-baseline QTcF, HR, PR, and QRS ( $\Delta\Delta\text{QTcF}$ , $\Delta\Delta\text{HR}$ , $\Delta\Delta\text{PR}$ , and $\Delta\Delta\text{QRS}$ ) across time points	LS mean and 90% CI from the statistical modeling will be shown by treatment (Section 6.5).
14.2.3.2.4.1	Scatter plot of QTcF versus RR by treatment	Scatter plots of QTcF and RR intervals by treatment with regression lines will be given (Section 6.2).
14.2.3.2.4.2	QTcF-RR quantile plot by treatment	QTcF-RR quantile plots (with quantiles) with linear mixed-effects line and 90% CI will be given (Section 6.2).
14.2.3.2.5.1	Plot of mean LOXO-292 plasma concentrations over time	Section 6.2.

Number	Title	Comments
14.2.3.2.5.2	Plot of mean moxifloxacin plasma concentrations over time	Section 6.3.
14.2.3.2.6	Joint plot of LOXO-292 plasma concentrations and $\Delta\Delta QTcF$ over time	Section 6.2.1.
14.2.3.2.7	Hysteresis plot of LOXO-292 plasma concentration and $\Delta\Delta QTcF$ connected in temporal order	This is what is often called a “Hysteresis plot” (Section 6.2.1).
14.2.3.2.8.1	Scatter plot of observed LOXO-292 plasma concentrations and $\Delta QTcF$ by subject	Scatter plot of $\Delta QTcF$ versus concentration with LOESS line and 90% CI and simple linear regression line (Section 6.2).
14.2.3.2.8.2	Scatter plot of observed LOXO-292 plasma concentrations and estimated placebo-adjusted $\Delta QTcF$ by subject	Scatter plot of estimated placebo-adjusted $\Delta QTcF$ versus observed concentration and linear mixed-effect regression line with CI (Section 6.2).
14.2.3.2.8.3	Scatter plot of observed moxifloxacin plasma concentrations and $\Delta QTcF$ by subject	Scatter plot of $\Delta QTcF$ versus concentration with LOESS line and 90% CI and simple linear regression line (Section 6.3).

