14.2.3.2.8.4	Scatter plot of observed moxifloxacin plasma concentrations and estimated placebo-adjusted $\Delta QTcF$ by subject	Scatter plot of estimated placebo-adjusted $\Delta QTcF$ versus concentration and linear mixed-effect regression line with CI (Section 6.3).
14.2.3.2.9.1	Model-predicted $\Delta\Delta QTcF$ (mean and 90% CI) and estimated placebo-adjusted $\Delta QTcF$ (mean and 90% CI) across deciles of LOXO-292 plasma concentrations	Section 6.2.
14.2.3.2.9.2	Model-predicted $\Delta\Delta QTcF$ (mean and 90% CI) and estimated placebo-adjusted $\Delta QTcF$ (mean and 90% CI) across deciles of moxifloxacin plasma concentrations	Section 6.3.
14.2.3.2.10.1	Predicted $\Delta\Delta QTcF$ interval at geometric mean peak LOXO-292 concentrations	Section 6.2.
14.2.3.2.10.2	Predicted $\Delta\Delta QTcF$ interval at geometric mean peak moxifloxacin concentrations	Section 6.3.
14.2.3.2.11.1	Scatter plot of standardized residuals versus fitted values for LOXO-292	Section 6.2.2.
14.2.3.2.11.2	Scatter plot of standardized residuals versus fitted values for moxifloxacin	Section 6.3.

Number	Title	Comments
14.2.3.2.12.1	Scatter plot of standardized residuals versus LOXO-292 concentrations with LOESS	Section 6.2.2.
14.2.3.2.12.2	Scatter plot of standardized residuals versus moxifloxacin concentrations with LOESS	Section 6.3.
14.2.3.2.13.1	Scatter plot of standardized residuals versus centered baseline QTcF with LOESS for LOXO-292	Section 6.2.2.
14.2.3.2.13.2	Scatter plot of standardized residuals versus centered baseline QTcF with LOESS for moxifloxacin	Section 6.3.
14.2.3.2.14.1	Box plot of standardized residuals versus nominal time for LOXO-292	Section 6.2.2.
14.2.3.2.14.2	Box plot of standardized residuals versus nominal time for moxifloxacin	Section 6.3.
14.2.3.2.15.1	Box plot of standardized residuals versus treatment for LOXO-292	Section 6.2.2.
14.2.3.2.15.2	Box plot of standardized residuals versus treatment for moxifloxacin	Section 6.3.
14.2.3.2.16.1	Normal Q-Q plot of standardized residuals for LOXO-292	Section 6.2.2.
14.2.3.2.16.2	Normal Q-Q plot of standardized residuals for moxifloxacin	Section 6.3.
14.2.3.2.17.1	Normal Q-Q plots of the estimated random effects for LOXO-292	Section 6.2.2.
14.2.3.2.17.2	Normal Q-Q plots of the estimated random effects for moxifloxacin	Section 6.3.

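### ECG SAP 6.2 computes the QTc bound at two geometric mean Cmax values but words a pass for every observed LOXO-292 concentration

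*SAP*

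**What the plan says.** ECG SAP 6.2 fits a linear mixed-effects model and takes the prediction with its two-sided 90% CI at the geometric mean Cmax of each LOXO-292 dose. The code has two ESTIMATE lines for this, one per dose. The higher is "ESTIMATE 'Pred Mean Diff for T2' TRT 1 CONC &GeoMeanCmax_2 / CL ALPHA=0.1". Table 14.2.3.1.10.1 gives the prediction for the "interval at geometric mean peak LOXO-292 concentration" and for no other concentration.

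The rule is met if the upper bound "is below 20 ms at clinically relevant plasma levels of LOXO-292". It then concludes that LOXO-292 "does not cause clinically concerning QTc prolongation within the observed plasma concentration ranges". The SAP does not define which plasma levels count as clinically relevant.

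Two planned figures go further up the concentration scale. Figure 14.2.3.2.8.2 plots estimated placebo-adjusted values "versus observed concentration and linear mixed-effect regression line with CI". Figure 14.2.3.2.9.1 shows predictions with 90% CIs "across deciles of LOXO-292 plasma concentrations". SAP 6.2 says that the quantile plot "will be used to evaluate the adequacy of the model fit to the assumption of linearity". No decision rule refers to either figure.

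Protocol 10.2 frames the primary endpoint at Cmax values for the exposures of interest. Protocol 15.3.2 step 6 also applies its 20 msec limit at the Cmax of a dose of interest, and says only when a positive effect is concluded.

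**The concern.** The condition is evaluated at two concentrations, and the conclusion is stated for all of them. If the slope is positive, the upper bound keeps rising above the supratherapeutic geometric mean. The rule could then declare no clinically concerning prolongation at observed concentrations where the same fitted model has an upper bound above 20 ms. The primary conclusion of the study would contradict its own regression and decile figures.

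The uncovered region matters. Protocol 9.2.2 chose the supratherapeutic dose to reach about twice the therapeutic Cmax, as expected with a strong CYP3A4 inhibitor. It also reports that this dose averaged slightly less than that, with 2 of 6 subjects at about twice. The exposure of greatest interest may therefore lie somewhat above the higher tested point.

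**Working it through.** The plan states no figure for this point, so there is none to reproduce. The check asks what a pass at two points guarantees, and how large the gap is.

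**1. What a pass covers.** Under the linear model the upper bound is U(C) = intercept + slope × C + t × √(quadratic in C). This is convex in C, ignoring small changes in degrees of freedom. If U is below 20 ms at both tested points, it is below 20 ms between them. From Protocol 9.2.2 the expected points are about 3300 ng/mL and 2 × 3300 = 6600 ng/mL. Nothing follows for concentrations above the higher point. Below the lower point there is no formal guarantee either, but with a positive slope that has little practical weight.

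**2. Where a passing bound reaches 20 ms.** Let U be the bound at the supratherapeutic geometric mean and a the intercept. Treating the bound as linear in concentration, it reaches 20 ms at the multiple k = (20 − a)/(U − a).

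| U (ms) | k, a = −3 | k, a = 0 | k, a = +3 |
|---|---|---|---|
| 12 | 1.53 | 1.67 | 1.89 |
| 15 | 1.28 | 1.33 | 1.42 |
| 18 | 1.10 | 1.11 | 1.13 |

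A generalised least squares version of the SAP model with zero intercept gives 1.64–1.65, 1.32–1.33 and 1.11, so 20/U is adequate.

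**3. How many subjects lie above that point.** The Cmax CV at this dose in healthy subjects is not given. I assume 18.6% to 41.6%, from two patient rows of Investigator's Brochure Table 5-1 (240 mg BID, n = 5; 160 mg BID, n = 251), and log-normal Cmax. Then σ = √ln(1 + CV²) = 0.184 to 0.400. The expected number of 30 subjects with Cmax above k is 30 × [1 − Φ(ln k/σ)], with k = 20/U:

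- U = 12 ms: 0.1 to 3.0 subjects
- U = 15 ms: 1.8 to 7.1 subjects
- U = 18 ms: 8.5 to 11.9 subjects

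**4. When the wording conflicts with the model.** The median of the highest of 30 values is at z = Φ⁻¹(0.5^(1/30)) = 2.00. That is exp(2.00σ) = 1.45 to 2.22 times the geometric mean. The bound there exceeds 20 ms once U exceeds 20/1.45 = 13.8 ms (low CV) or 20/2.22 = 9.0 ms (high CV). At the 90th percentile of Cmax (1.27 to 1.67 times) the thresholds are 15.8 and 12.0 ms.

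**5. The planned case.** SAP 6.6 assumes a 3 ms difference, a within-subject SD of 8 ms and 30 evaluable subjects. I placed the 3 ms at the supratherapeutic geometric mean and calculated the bound from the SAP 6.2 model. The inputs were 12 time points, placebo plus two doses, residual SD 8, an assumed between-subject SD of 4, zero intercept, an assumed concentration profile, and a range of slope variability and residual correlation. The bound is about 4.1 to 5.4 ms at that point and about 6.4 to 12.1 ms at the typical highest Cmax. Both are below 20 ms.

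**The case against.** The case for leaving the text alone has several parts.

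- **The trigger does not literally name the two geometric means.** This is correct. The two-point reading is an inference from the preceding sentences, the code and the table. No other level is specified anywhere, so it is the only workable reading. The missing definition is part of the defect.
- **The higher point already represents the planned worst case, and any geometric mean is exceeded by about half of the individual values.** Also correct. This defends the test, which should stay. It does not defend a conclusion that reaches beyond the test.
- **The figures will show any bound above 20 ms.** They will, but their stated role is model checking. They would display the contradiction without resolving it.
- **Speaking of the observed range may only guard against extrapolation, and Protocol 9.2.1 uses similar language.** The protocol text is background and sets no test. As a guard against extrapolation the phrase still covers every observed concentration.
- **A nonlinear model may replace the linear one.** SAP 6.2.2 says "The concentration-QTc analysis will then be repeated for the model found to best accommodate the nonlinearity detected". The multiples above would then differ, but the mismatch in scope would remain.

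A reader might also infer that the SAP overrides a narrower pass statement in protocol step 6. The documents do not support that, because step 6 contains no pass statement. The comparison shows only that the protocol frames its limit at Cmax values of interest.

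**Conclusion.** The point holds as a mismatch between what is tested and what is concluded for the primary endpoint. With a positive slope, the rule as written can state no concern at observed concentrations where its own model's 90% upper bound exceeds 20 ms. This happens at the typical highest of 30 Cmax values once the bound at the supratherapeutic geometric mean exceeds about 9 to 14 ms, and at the 90th percentile once it exceeds about 12 to 16 ms. These thresholds rest on a linear model, a near-zero intercept, log-normal Cmax and CVs borrowed from patients at steady state.

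A reader might infer that the planned study would reach a wrong verdict. The figures do not support that. Under the planned 3 ms effect the bound stays below 20 ms across the likely range of Cmax. A single-time-point paired calculation, 3 + 1.699 × 8 × √(2/30) = 6.5 ms, overstates the bound, because the SAP model pools time points and doses. The problem arises only with a larger effect, but a prespecified rule has to be sound in that case too. The wording should be changed; the test need not be.

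**What to change.** In ECG SAP 6.2:

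1. Keep the predictions at the two geometric mean Cmax values as the test, and define *clinically relevant plasma levels* as those two values.
2. Report from the final model, linear or its nonlinear replacement, the highest observed concentration X at which the 90% upper bound stays below 20 ms.
3. Word the conclusion as applying *up to X ng/mL*, or limit it to the two tested exposures, in place of the observed-range phrase.

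This costs one reported number and a change of wording. It needs no new data and no new pass/fail criterion, and the planned code already requests the estimates and their covariance matrix. The downside is that the conclusion may cover less than the full observed range. X also depends on the data, so it should be reported as a description of where the bound holds and not as a second test.

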### 6.2.1 Investigation of Hysteresis

Hysteresis will be assessed based on joint graphical displays of the least squares (LS) mean difference between  $\Delta QTcF$  under LOXO-292 and under placebo ( $\Delta\Delta QTcF$ ) for each post-dose time point from the by-time point analysis and the mean concentration of LOXO-292 at the same time points. In addition, hysteresis plots will be given for LS mean  $\Delta\Delta QTcF$  from the by-time point analysis and the mean concentrations. If a QT effect  $> 20$  ms (i.e., LS mean  $\Delta\Delta QTcF > 10$  ms) cannot be excluded and the mean peak  $\Delta QTcF$  effect is observed at the same time point and the delay between peak plasma levels and peak QT effect of more than 1 hour is present, other concentration-QTc models such as a model with an effect compartment may be explored. With the provision stated above, hysteresis will be assumed if the curve of hysteresis plot shows a counterclockwise loop. A significant treatment effect-specific intercept is not biologically plausible and therefore may be indicative of hysteresis, if it cannot be explained by a nonlinear relationship.

